## 7.5 Efficacy analyses

This section addresses separately the analyses to be conducted on the efficacy variables measured in this study.

### 7.5.1 Analysis methods

All efficacy outcomes will be analysed by descriptive statistics only. No statistical tests will be performed.

### 7.5.2 Analysis of efficacy endpoint(s)

#### For patients with diagnosis PID or SID:

For each fourth infusion visit (starting with infusion visit 4) and the close-out visit the influence of the treatment with IVIG/SCIG on the frequency, intensity and duration of infections and the consumption of antibiotics since the last visit is recorded. Possible outcomes are beneficial, unchanged and unfavorable. Counts and percentages of these outcomes will be summarized by infusion visit and for the close-out visit by treatment group and overall in the Safety population. In addition, the patient's last available assessments will be summarized. These summaries will be generated for the pool of PID/SID patients and for each of the two diagnoses separately.

For each fourth infusion visit (starting with infusion visit 4) and the close-out visit the occurrence of new infectious episodes (yes/no) since the last visit is recorded. In case of the occurrence of new infectious episodes patients are asked regarding the infected area and the number of infectious episodes in this area using the following pre-specified categories:

- Serious infections of the upper respiratory tract

- Serious infections of the lower respiratory tract
- Urinary tract infections
- Bacteremia/sepsis
- Bacterial meningitis
- Osteomyelitis/septic arthritis
- Bacterial pneumonia
- Visceral abscesses
- Other infectious diseases

The number and percentage of patients with new infectious episodes since the last visit and the number and percentage of patients with new infectious episodes in each of the above categories will be summarized by infusion visit and for the close-out visit by treatment group and overall in the Safety population. In addition, this summary will be generated for the patient's last available assessment.

Further the occurrence of any infectious episodes during the course of the study, the occurrence of any infectious episodes in each of the above categories during the course of the study, the total number of infectious episodes and the total number of infectious episodes in each of the above categories will be summarized by treatment group and overall in the Safety population. These summaries will be generated for the pool of PID/SID patients and for each of the two diagnoses separately.

As cases of bacterial pneumonia actually are always recorded as cases of serious infections of the lower respiratory tract as well, the former will not be counted in the calculation of the total number of infectious episodes.

In case that a certain type of infection has occurred but the pertaining number of infectious episodes is missing this number will be set to one.

According to the study protocol (section 3.1.4) the individual duration of the study should be at least 12 months for patients with diagnosis PID or SID. To evaluate the efficacy for patients who fulfill this condition the analyses described above will be repeated in this subgroup. To evaluate the efficacy for patients who do not fulfill this condition but are at least 6 months in the study the analysis will also be repeated for patients with a study duration of at least 6 months but less than 12 months.

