3.1.4 Study Duration

This study started in August 2011 in 4 European countries and was then extended to Canada. The European centres are now closed or being closed and the study will continue in Canada. Planned study end is 2022.

The duration of observation for an individual patient will be as long as any of the described IVIGs or the SCIG will be prescribed by the treating physician and until the next regularly scheduled visit of the patient after last infusion. For patients with PID or SID the observation period should last at least 12 months, if possible.

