### **7.2 Patient disposition**

Patient disposition information will be summarized by treatment group and overall. The number of patients who were enrolled will be shown in the overall summary, further the number and percentage of patients who received at least one infusion with study drug, who ended the study but continued treatment with study IVIG/SCIG and who terminated treatment with study IVIG/SCIG will be presented. The primary reason for early withdrawal will also be tabulated. The number of patients treated will be used as the denominator for the percentage calculation.

A table of patient disposition will also be generated by study centre and country.

The study duration (in months) of an individual patient will be calculated as (Maximum(Date of close-out visit, date of last infusion with IVIG/SCIG) - Date of first infusion with IVIG/SCIG + 1)/30.4375 and will be summarized by treatment group and overall in the Safety population.

Patient disposition will be listed.

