### 7.3.2 Baseline and disease characteristics

The underlying diagnosis and its severity as assessed by the investigator will be summarized by treatment group and overall in the Safety population. For the diagnosis the following pre-specified categories will be considered if at least one patient with this diagnosis is included in the Safety population:

- Primary Immunodeficiency (PID)
- Secondary Immunodeficiency (SID)
- Immune Thrombocytopenic Purpura (ITP)
- Guillain-Barré Syndrome (GBS)
- Chronic Inflammatory Demyelinating Polyradiculoneuropathy (CIDP)
- Multifocal Motor Neuropathy (MMN)
- Myasthenia Gravis (MG)
- Multiple Sclerosis (MS)
- Dermatomyositis (DM)
- Polymyositis (PM)
- Pemphigus Vulgaris (PV)
- Toxic Epidermal Necrolysis (TEN)
- Other.

The presence of pre-specified concomitant diseases/risk factors at baseline will be summarized descriptively by treatment group and overall in the Safety population. The following concomitant diseases/risk factors will be considered:

- History of previous thromboembolic events (yes/no)
- Atherosclerosis (yes/no)
- Coronary artery disease (yes/no)
- Impaired cardiac output (yes/no)
- Obesity (yes/no)
- Diabetes (yes/no)
- Hypertension (yes/no)

- Hyperlipidemia (yes/no)
- Coagulation disorders (yes/no)
- In-dwelling catheters or devices (yes/no)
- Immobilization (yes/no)
- Known or suspected blood hyperviscosity (yes/no)
- Other cardiovascular risk factor(s) (yes/no)
- Other relevant concomitant diseases (yes/no).

Previous thromboembolic events and other relevant concomitant diseases will be coded by MedDRA Version 23.0 or higher and summarized by System Organ Class (SOC) and Preferred Term (PT) in the Safety population. The sort order will be by decreasing frequency in the overall group by SOC and then by PT within SOC. These summaries will also be generated by diagnosis.

For patients with diagnosis PID or SID the history of recent infectious episodes within the last 12 months before study observation start is recorded in the eCRF. In case any recent infectious episodes have been observed, patients are asked regarding the infected area and the number of infectious episodes in this area using the following pre-specified categories:

- Serious infections of the upper respiratory tract
- Serious infections of the lower respiratory tract
- Urinary tract infections
- Bacteremia/sepsis
- Bacterial meningitis
- Osteomyelitis/septic arthritis
- Bacterial pneumonia
- Visceral abscesses

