- Other infectious diseases.

The occurrence of any recent infectious episodes, the occurrence of any recent infectious episodes in each of the above categories, the total number of recent infectious episodes and the total number of recent infectious episodes in each of the above categories will be summarized by treatment group and overall in the Safety population. These summaries will be generated for the pool of PID/SID patients and for each of the two diagnoses separately.

As cases of bacterial pneumonia actually are always recorded as cases of serious infections of the lower respiratory tract as well, the former will not be counted in the calculation of the total number of recent infectious episodes.

In case that a certain type of infection has occurred but the pertaining number of infectious episodes is missing this number will be set to one.

All baseline and disease characteristics will be listed.

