**7.7 Other analyses****7.7.1 Subgroup analysis**

All summaries will also be generated by the underlying diagnosis. In addition, summaries of ICSRs and ADRs will also be generated by country (Austria, Spain, France, UK and Canada) and by age group (age categories < 18, 18-43, 44-68, and > 68 years).

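### PID/SID infection totals over the study have no person-time denominator, although follow-up is open-ended and the matching baseline count covers a fixed 12 months

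*SAP*

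**What the plan says.** SAP 7.5.2 (PID or SID) summarises two things over the whole study by treatment group and overall: whether any infectious episode occurred, and how many. In its words, "the total number of infectious episodes and the total number of infectious episodes in each of the above categories will be summarized". The same is done for each of nine infection categories, and for PID, SID and the pool. Neither document defines an infection rate or a patient-year denominator.

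Protocol 3.1.4 sets follow-up: "The duration of observation for an individual patient will be as long as any of the described IVIGs or the SCIG will be prescribed". For PID and SID it asks for at least 12 months where possible and gives no maximum.

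At baseline (SAP 7.3.2), "the history of recent infectious episodes within the last 12 months before study observation start is recorded in the eCRF". The same nine categories are tabulated in the same form: "the total number of recent infectious episodes and the total number of recent infectious episodes in each of the above categories will be summarized".

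Three other parts of the SAP bear on the point.

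- **Duration subgroups (7.5.2).** For PID/SID patients with at least 12 months in the study, "the analyses described above will be repeated in this subgroup". In addition, "the analysis will also be repeated for patients with a study duration of at least 6 months but less than 12 months".
- **Study duration (7.2).** "The study duration (in months) of an individual patient will be calculated as" the time from first infusion to the later of close-out visit and last infusion. It is summarised by treatment group and, under 7.7.1, by diagnosis ("All summaries will also be generated by the underlying diagnosis").
- **By-visit summaries (3.5 and 7.5.2).** At every fourth infusion visit and at close-out, the percentage of patients with a new infection since the last visit is shown. This, and not the study-course total, is the listed secondary endpoint.

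**The concern.** A cumulative count grows with the time over which it is collected, and so does the proportion of patients with at least one event. Here that time varies from patient to patient without an upper limit. It may also differ between treatment columns: the study began in 2011, while Protocol 1.1 dates the first panzyga approvals to 2016 and calls cutaquig newly licensed. The documents give no follow-up by product, so neither the size nor the direction of any imbalance is known.

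Two misreadings are at stake. Columns with the same infection rate can look different. And because the baseline table has the same layout over 12 months, a reader who sets the two tables side by side can miss a real fall or rise, or see it reversed. In a descriptive study the tables are the result, so a table that confounds rate with follow-up matters even without a test.

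The point is confined to the study-course totals and any-infection summaries in PID/SID. It does not touch the beneficial/unchanged/unfavorable ratings or the outcomes in other diagnoses.

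**Working it through.** **Plan's own figure.** There is none to reproduce. SAP 4 reports no sample size calculation, and neither document gives an infection rate or an observed follow-up time.

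**Assumptions.** Infection rates of 0.5, 1 and 2 per patient-year, constant over time and equal across patients (Poisson), with infections captured continuously.

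**Formulas.** Expected total per patient = rate × months/12. Proportion with any infection = 1 − exp(−rate × months/12).

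**1. Equal rates, different follow-up, within each duration subgroup.**

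| Rate per year | Total, 12 vs 36 months | Any infection, 12 vs 36 months | Any infection, 6 vs 11.9 months |
|---|---|---|---|
| 0.5 | 0.5 vs 1.5 | 39.3% vs 77.7% | 22.1% vs 39.1% |
| 1 | 1.0 vs 3.0 | 63.2% vs 95.0% | 39.3% vs 62.9% |
| 2 | 2.0 vs 6.0 | 86.5% vs 99.8% | 63.2% vs 86.2% |

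The 12-versus-36-month totals differ by 36/12 = 3 at every rate. In the lower subgroup the spread is 11.9/6 = 1.98, almost twofold. The upper subgroup has no ceiling; August 2011 to an assumed December 2022 is 137 months. Patients with under 6 months have no subgroup of their own.

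**2. On-study total against the 12-month baseline count.** Ratio = (on-study rate / baseline rate) × months/12, so the baseline rate cancels.

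- Halved rate: 0.5 × months/12 = 0.25, 0.5, 1.0, 1.5 and 2.5 at 6, 12, 24, 36 and 60 months.
- Doubled rate at 6 months: 2 × 6/12 = 1.0.

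So a true halving shows no change at 24 months and an apparent rise at 36, while a true doubling shows no change at 6 months.

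**3. Dependence on the capture window.** Assessments fall at every fourth infusion visit. If 'since the last visit' means since the preceding infusion visit, then roughly one quarter of the time is captured, ignoring close-out. The halved-rate ratios become about 0.06, 0.13, 0.25, 0.38 and 0.63: no reversal, but a large apparent fall. The threefold ratio in step 1 is unaffected if the captured fraction is the same in both columns.

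**4. What the planned duration summary allows.** For patients on one product, total episodes divided by (n × mean study duration) gives a crude rate. It cannot be formed within the subgroups from the planned tables, because 7.5.2 repeats only its own analyses there. Nor can it be formed by product in a composed (switcher) group under SAP 7.1, because each patient has a single, unsplit duration.

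**5. Effect of a person-time denominator.** At 1 per year, 100 patients followed for 12 months give 100 episodes in 100 patient-years. Followed for 36 months, they give 300 in 300. Both are 1.0 per patient-year, on the same scale as the baseline year.

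**The case against.** The strongest reply is that the defined endpoint is not affected. SAP 3.5 lists infections since the last visit, and those by-visit percentages do not accumulate with total follow-up; the study-course totals are an addition. That stands, and it limits the weight of the point. It does not replace a rate, however. The percentages count patients and not episodes, and SAP 3.3 rules out predefined visit times, so the windows have no fixed length.

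Second, SAP 7.5.1 is descriptive only, and no change from baseline is planned. A reader might infer that the SAP will draw a wrong conclusion about efficacy against baseline. The documents do not support that: the baseline counts sit under baseline characteristics, and the comparison would be the reader's own. The identical layout invites it all the same.

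Third, a reader might infer that treatment columns will differ threefold. That would need mean follow-up to differ threefold, for which there is no evidence. Variation between patients would also narrow the any-infection contrast. With a gamma-distributed rate of mean 1 per year and dispersion 1 (an assumption), 1 − 1/(1 + months/12) gives 50% versus 75% at 12 and 36 months, not 63% versus 95%.

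Fourth, all efficacy outcomes and infusion details are listed, so rates could be worked out by hand. That is true, but it leaves the derivation to each reader. The SAP already accepts an exposure denominator for ADRs (number of infusions, 7.6.1).

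**Conclusion.** The point holds for the study-course infection totals and any-infection summaries in PID/SID. They mix rate with length of observation, and the duration subgroups and separate duration summary remove this only in part. The change should be made, but the point is modest: the affected tables are supplementary, descriptive and secondary.

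The threefold difference at 12 versus 36 months rests on a constant rate and equal capture in both columns; differences will be smaller where mean follow-up differs less. The baseline ratios of 0.5, 1.0 and 1.5 for a halved rate also require continuous capture, which the SAP wording leaves open. The any-infection percentages further depend on the assumed rates and on a common rate across patients. The documents do not show that any column difference or baseline reversal will in fact occur.

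**What to change.** 1. **Settle the capture window first.** Confirm from the eCRF whether 'since the last visit' refers to the previous infection assessment or to the preceding infusion visit. In the first case, covered person-time runs from first infusion to the last infection assessment; this can be shorter than study duration, since Protocol 4.1 asks only for efforts to arrange a close-out visit. In the second, only the captured intervals count, and the by-visit percentages should be labelled accordingly.
2. **Add a rate to SAP 7.5.2.** Keep the raw counts and add total episodes divided by total covered patient-years, overall and per category, for PID, SID and the pool, by treatment group and within both duration subgroups.
3. **Show the 12-month baseline count as a rate beside it.** Note that the baseline year may include prior immunoglobulin (SAP 7.3.3) and that any change is descriptive.
4. **Only if composed groups are formed (SAP 7.1),** assign the episodes and person-time of each assessment interval together to one product, and show intervals that straddle a switch separately. Dropping them should not be called negligible. At an assumed 21 to 28 days between infusions, four infusions span 84 to 112 days, or 2.76 to 3.68 months (÷ 30.4375). That is about 8% to 10% of 36 months, 23% to 31% of 12 months and 46% to 61% of 6 months.

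The cost is SAP wording, the eCRF check, one derivation from infusion dates, visit dates and product per infusion, and extra table rows. No new data are collected.

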### 6.2 Handling of missing data and outliers

#### 6.2.1 Missing data analysis methods

For the handling of missing numbers of infections, see sections 7.3.2 and 7.5.2. Missing values of body weight in the calculation of measures of exposure will be handled as described in section 7.4.2. Otherwise, missing data will not be imputed for any analysis. For the handling of missing or incomplete start and end dates of Individual Case Safety Reports and medications, see section 6.2.2.

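### Setting a missing lower respiratory count to one, with pneumonia left out, can push the overall infection total below the minimum the SAP's own premise implies

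*SAP*

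**What the plan says.** For PID/SID patients, SAP 7.5.2 records new infections by category: "patients are asked regarding the infected area and the number of infectious episodes in this area using the following pre-specified categories". Serious LRTI and bacterial pneumonia are two separate entries in that list, each with its own number.

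The planned output is an overall total beside the category totals: "the total number of infectious episodes and the total number of infectious episodes in each of the above categories will be summarized".

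Two rules then govern the overall total.

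- **Exclusion.** The premise is stated as fact: "As cases of bacterial pneumonia actually are always recorded as cases of serious infections of the lower respiratory tract as well". From it follows that "the former will not be counted in the calculation of the total number of infectious episodes".
- **Missing number.** Where a type of infection is marked as having occurred but "the pertaining number of infectious episodes is missing this number will be set to one".

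SAP 7.3.2 applies the same pair of rules to the 12-month history before study start; there too, "the former will not be counted in the calculation of the total number of recent infectious episodes". The general missing-data section, SAP 6.2.1, adds nothing further: "For the handling of missing numbers of infections, see sections 7.3.2 and 7.5.2".

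No text makes the exclusion depend on an LRTI entry or number being present, compares the two counts, or uses a recorded pneumonia number when the LRTI number is missing.

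**The concern.** Each rule is reasonable alone, but together they can conflict. The exclusion is safe only if the LRTI number already contains every pneumonia. The missing-number rule can replace that LRTI number with 1 whatever pneumonia count stands next to it. A form can then report several pneumonias while the overall total counts one lower respiratory episode. By the SAP's own premise, that imputed value is impossible.

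A second gap arises if the premise fails on a form. A pneumonia entered without an LRTI entry makes the patient a yes for infectious episodes but adds nothing to the total number.

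At stake is the internal consistency of a planned descriptive summary. SAP 7.5.2 produces it for PID and SID pooled and separately, and repeats it for patients with at least 12 months, and with 6 to under 12 months, in the study. Both failures lower the total, and neither would be flagged by the rules as written.

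**Working it through.** The documents state no figure on this point, so there is none to reproduce. The check applies the two rules to possible forms.

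**Notation, for one form**

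- L = LRTI number, P = bacterial pneumonia number, O = episodes in all other categories (the category list in SAP 7.5.2).
- L* = L if recorded; 1 if LRTI is ticked and the number is missing; 0 if LRTI is not ticked. A ticked pneumonia with a missing number likewise becomes P = 1.
- SAP total = L* + O, since pneumonia is excluded.
- Larger-count total = max(L*, P) + O.

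**Step 1: complete forms.** With L = 3, P = 2, O = 0, the SAP total is 3. A plain sum would give 3 + 2 = 5 and count two episodes twice. The exclusion works as intended.

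**Step 2: LRTI ticked, number missing, premise true.** If every pneumonia is also an LRTI, the true LRTI number is at least P, so the true total is at least P + O. The SAP total is 1 + O. The shortfall is therefore at least (P + O) − (1 + O) = P − 1, which is above zero whenever P is 2 or more.

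**Step 3: when the conflict shows on the form itself.** The total is below the pneumonia count when 1 + O < P, that is, when P ≥ 2 + O.

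**Step 4: worked cases**

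| LRTI entry | P | O | SAP total | Larger-count total |
|---|---|---|---|---|
| 3 | 2 | 0 | 3 | 3 |
| 2 | 2 | 0 | 2 | 2 |
| 3 | missing, so 1 | 0 | 3 | 3 |
| ticked, number missing | missing, so 1 | 0 | 1 | 1 |
| ticked, number missing | 1 | 0 | 1 | 1 |
| ticked, number missing | 2 | 0 | 1 | 2 |
| ticked, number missing | 3 | 0 | 1 | 3 |
| ticked, number missing | 3 | 1 | 2 | 4 |
| ticked, number missing | 3 | 2 | 3 | 5 |
| not ticked | 1 | 0 | 0 | 1 |
| not ticked | 2 | 0 | 0 | 2 |

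In the row with P = 3 and O = 2, the SAP total of 3 is not below the pneumonia count, so nothing looks odd, but it is still short by 2. The last two rows are the case where the premise fails.

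**Step 5: enumeration with the premise kept.** Let LRTI always be ticked, L be missing or 1 to 5, P be missing or 1 to 5, and O be 0 to 3, with L ≥ P whenever both are recorded. The SAP total falls below P in exactly 10 combinations, all with the LRTI number missing: (P, O) = (2,0), (3,0), (3,1), (4,0), (4,1), (4,2), (5,0), (5,1), (5,2), (5,3). It never does so when P = 1, when both numbers are missing, or when only the pneumonia number is missing.

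**The case against.** The strongest reply is that this is a data-entry edge case already dealt with upstream. Protocol 7.1 has eCRF data checked and queried for gaps and implausible values, and obliges investigators to supply them. An LRTI entry without a number, or a pneumonia without an LRTI, is what such queries should catch. This stands as a reason to expect few cases. It does not remove the point, because the SAP provides for numbers still missing at analysis and the value it then assigns can contradict its own premise.

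It is also fair that the exclusion is right on complete forms, and that where the total falls below the pneumonia count the mismatch would be visible beside the category totals.

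A reader might infer more than the documents support:

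- **That pneumonia disappears from the efficacy results.** It keeps its own category total and its yes/no and by-visit summaries, and all efficacy outcomes are listed.
- **That a main endpoint is biased.** SAP 3.5 names the rated influence of treatment and the occurrence of infectious episodes, not a total count. Efficacy is a secondary objective, analysed descriptively without tests.
- **That a before/after comparison is distorted.** Neither SAP 7.3.2 nor 7.5.2 specifies one.
- **That the premise cannot hold for later forms**, since the SAP is dated 14 April 2020 and Protocol 3.1.4 plans the study end for 2022. If double entry is built into the eCRF, it holds for later forms too. The eCRF is not in the documents, so this cannot be settled either way.

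**Conclusion.** The point holds as a small inconsistency between two stated rules. With LRTI ticked, its number missing and pneumonia recorded as 2 or more, the overall total is too low by at least the pneumonia count minus 1. This needs only the SAP's own premise. The second failure, a pneumonia lost because no LRTI was entered, depends on that premise failing on a form, which the documents neither show nor rule out.

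The error is always an undercount. It is zero where the LRTI number is present and at least as large as the pneumonia count. The number of affected forms cannot be derived from the documents. Given the query process and the specific trigger, the effect is probably small. It bears on a descriptive total and not on the study's primary safety endpoint.

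**What to change.** In SAP 7.3.2 and 7.5.2, for the baseline history and for each on-study assessment:

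1. If LRTI is ticked and its number is missing, set it to the larger of 1 and the pneumonia count.
2. Use the larger of the LRTI and pneumonia counts as the lower respiratory contribution to the overall total.
3. Report how many counts were imputed.

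Apply step 2 to each assessment before summing over a patient's visits. Take two forms: LRTI number missing with pneumonia 3, and LRTI 3 with pneumonia 2. Form by form, the contributions are 3 + 3 = 6. Under the current set-to-one rule the summed counts are LRTI 1 + 3 = 4 and pneumonia 3 + 2 = 5, and taking the larger of those sums gives only 5.

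The cost is about one line of wording and code in each section. The guard against double counting stays. Totals are unchanged wherever the LRTI number is present and at least the pneumonia count. It would be wrong to say they are unchanged whenever the premise holds: with LRTI missing and pneumonia 3 the premise can be true, and the total still moves from 1 to 3.

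The change has one limit. If recorded LRTI and pneumonia episodes were in fact distinct, say 3 and 2, the larger count still gives 3 and not 5. Only a data query can resolve that.
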